The control group will receive standard care, including the use of the ABCDEF bundle (Appendix 1) daily, which involves delirium screening using the Confusion Assessment Method-Intensive Care Unit (CAM-ICU) score (Appendix 2), but will not have routine psychiatric involvement in care. The CAM-ICU is performed by the ICU nurses on a daily basis. It consists of several questions that assess patient's mental status, if the change in mental status fluctuates, the sedation score (using Richmond Agitation Sedation Score [RASS]), and the patient's attention span and if disorganized thinking is present by asking several questions. The CAM-ICU can be performed in intubated patients by asking the patient to follow commands with their hands, or squeeze the nurse's hand in response to a question. The CAM-ICU will be done every morning, but may also be repeated later on in the day if the patient's mental status changes from the morning-this will be the same for both the control and intervention group. Enrollment and data collection will continue for as long as it takes to reach the target sample size of 52 patients for this group. We will then provide standard care (including ABCDEF bundle implementation, which is standard practice in 7W ICU) and provide routine psychiatric care, which entails a member of the psychiatric team (attending, resident, and/or fellow) participating in daily (Monday-Friday) multidisciplinary rounds with the ICU team (intervention group); the psychiatry team will help provide nonpharmacological and pharmacological intervention strategies in patients diagnosed with delirium and help distinguish delirium from other psychiatric disorders which may be missed by the ICU team and provide earlier treatment of these conditions. This study phase will continue until the target sample size of 52 patients is reached.

In both the control and intervention groups, delirium will be diagnosed by a positive CAM-ICU score. Both groups will have the CAM-ICU test administered by the patient's nurse on a daily basis (which is standard practice in 7W ICU) in the morning and may be repeated later on in the day if the patient's mental status changes. Data on the incidence of ICU delirium, duration of delirium/mechanical ventilation, in-house mortality, hospital and ICU length of stay will be collected.

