Additionally, we will collect the following data: age, gender, body mass index, history of alcohol or substance abuse, admitting diagnosis, dementia, comorbid conditions, admitting Sequential Organ Failure Assessment (SOFA) score, deliriogenic medications used during study enrollment, the interventions/medications used to treat delirium as designated by psychiatry and the ICU team (in intervention group) and the ICU team (control group), and the number of days from ICU admission to study enrollment. We will input data into a secure, password protected, encrypted, electronic database, RedCap.

The data points will be compared between the control and intervention groups (see section 13.0).

Our primary outcome is: incidence of ICU delirium.

The secondary outcomes are: duration of delirium/mechanical ventilation, in-house mortality, and hospital and ICU length of stay.

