#### **5.0 SELECTION AND WITHDRAWAL OF SUBJECTS**

Inclusion criteria are:

1. Patients who are  $\geq 18$  years of age
2. Patients admitted to the surgical ICU for  $>48$  hours OR
3. Patients admitted to the ICU  $<24$  hours who have been in the hospital  $>48$  hours OR
4. Patients who return to the ICU after being discharged from the ICU to the floor due a complication or need for higher acuity care.
5. Patients admitted to any surgical service who are receiving care in the 7 West surgical ICU, who are either medically or conservatively managed (non-surgical) or surgically managed as part of their care

Exclusion criteria are:

1. Patients in whom CAM-ICU cannot be performed (severe dementia, stroke or other neurological condition, encephalopathy, mental retardation, severe psychiatric disorder, vegetative state, severe traumatic brain injury, deaf/blind, etc.)
2. Patients who don't speak or understand English
3. Current alcohol or substance abuse
4. Patients who already have delirium within 24-48 hours of their ICU admission [Defined as a positive CAM-ICU test, or based on the *Diagnostic and Statistical Manual of Mental Disorders, Fifth Edition (DSM-V)* diagnostic criteria:

- Disturbance in attention (ie, reduced ability to direct, focus, sustain, and shift attention) and awareness.
- Change in cognition (eg, memory deficit, disorientation, language disturbance, perceptual disturbance) that is not better accounted for by a preexisting, established, or evolving dementia.
- The disturbance develops over a short period (usually hours to days) and tends to fluctuate during the course of the day.

- There is evidence from the history, physical examination, or laboratory findings that the disturbance is caused by a direct physiologic consequence of a general medical condition, an intoxicating substance, medication use, or more than one cause.]

Patients will be screened for eligibility on rounds daily. Patients may withdraw from the study at any point without impacting their healthcare.

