## **6.0 STRATIFICATION/DESCRIPTIVE FACTORS/RANDOMIZATION SCHEME**

This is a prospective, single institution, controlled, pilot study of patients admitted to the 7W ICU. A sample size of 104 (52 per group) is targeted. Patients will be screened for study eligibility on a daily basis. The control group will undergo standard ICU care, which includes the use of the ABCDEF bundle (Appendix 1) daily, which involves delirium screening using the CAM-ICU tool (Appendix 2), but will not have routine psychiatric involvement in care. Enrollment and data collection will continue for as long as it takes to reach the target sample size of 52 patients for this group. We will then proceed to enroll patients into the intervention group, who undergo standard care (including ABCDEF bundle implementation, which is standard practice in 7W ICU) in addition to a psychiatric team intervention, which entails having a member of the psychiatric team (attending, resident, and/or fellow) participate in daily (Monday-Friday) multidisciplinary rounds with the ICU team; they will help provide nonpharmacological and pharmacological intervention strategies in patients diagnosed with delirium and help distinguish delirium from other psychiatric disorders which may be missed by the ICU team and provide earlier treatment of these conditions. This study phase will continue until the target sample size of 52 patients is reached.

Data will be collected for both the control and intervention groups (see Section 12) and compared.

Randomization is not possible for this study; although block randomization was considered, it will result in sub-optimal data subject to bias.

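### The switch to psychiatry rounds is tied to reaching 52 controls, not to those controls having left the ICU, so late-enrolled controls can receive the intervention while counted as controls

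*Combined protocol and SAP*

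**What the plan says.** Section 3.0 states when the control phase ends: "Enrollment and data collection will continue for as long as it takes to reach the target sample size of 52 patients for this group". Its next sentence begins the second phase: "We will then provide standard care (including ABCDEF bundle implementation, which is standard practice in 7W ICU) and provide routine psychiatric care". Section 6.0 repeats the order: "We will then proceed to enroll patients into the intervention group". None of these places states a gap, a requirement that controls have been discharged, or a rule for patients who are in the unit on the day of the switch.

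The intervention is a change to how the unit rounds. Section 3.0 describes a psychiatry team member "participating in daily (Monday-Friday) multidisciplinary rounds with the ICU team", and nothing limits this to patients enrolled in the second phase. The same section defines controls as having no routine psychiatric involvement.

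Three parts of Section 5.0 bear on patients near the switch:

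- One entry route begins "Patients admitted to the surgical ICU for" and requires more than 48 hours, so these patients are in the unit before they enrol.
- Another route admits "Patients who return to the ICU after being discharged from the ICU to the floor", with no rule on former controls.
- An exclusion covers "Patients who already have delirium within 24-48 hours of their ICU admission". It does not refer to the phase switch.

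The data list in Sections 3.0 and 12 includes "the number of days from ICU admission to study enrollment". It lists neither the date of the switch nor the days each patient was exposed to psychiatry rounds.

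**The concern.** The groups are defined by calendar phase, and the intervention reaches everyone in the unit once it starts. A control enrolled shortly before the switch and still in 7W would therefore be rounded on by psychiatry and analysed as a control.

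Section 13.0 gives the pilot three purposes: feasibility, the base incidence of delirium, and the size of the intervention effect, all for planning a larger trial. If the intervention prevents delirium, exposed controls lower the estimated base incidence and shrink the estimated effect.

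The secondary outcomes are open to the same problem. A control who is already CAM-ICU positive can no longer change the primary outcome. But Sections 3.0 and 7.0 give psychiatry a role in treating delirious patients, so that control's delirium duration, ventilation days, length of stay and survival could still change.

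The planned analysis does not repair this. The inverse-probability weighting in Section 13.0 balances covariates between the labelled groups. It cannot correct a patient who spent time under both conditions.

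**Working it through.** **1. The plan's own figures (Section 13.0).** Inputs: 40% control incidence, a 25-point reduction (so 15%), and 47 per group.

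- Standard error of the difference = √[(0.40×0.60 + 0.15×0.85)/47] = √(0.3675/47) = 0.0884.
- 95% interval = 25 ± 1.96×8.84 = 25 ± 17.3 points, or 7.7% to 42.3%. The plan states 8%-42%, so it reproduces. It also confirms that the 25% is used as percentage points.
- Base rate: the exact (Clopper-Pearson) interval at 40% of 47 is 26.0% to 55.3%. The plan states 26%-55%.
- Drop-out: 94×1.1 = 103.4, rounded up to 104, or 52 per group.

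The last line matters here. The 52 is an enrolled count (47 plus a drop-out allowance), not a count of patients who have completed follow-up. This favours reading the trigger as enrolment.

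**2. Controls still in the ICU at the switch.** With steady accrual, the expected number is the enrolment rate multiplied by the mean ICU days after enrolment. Both inputs are assumptions, because the documents give neither. As a share of 52, the result is simply stay divided by accrual time.

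| Accrual of 52 controls | ICU days after enrolment | Exposed controls | Share |
|---|---|---|---|
| 3 months (91 days) | 5 | 52/91×5 = 2.9 | 5.5% |
| 3 months (91 days) | 10 | 52/91×10 = 5.7 | 11.0% |
| 6 months (183 days) | 5 | 52/183×5 = 1.4 | 2.7% |
| 6 months (183 days) | 10 | 52/183×10 = 2.8 | 5.5% |

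**3. Effect on the primary difference.** Observed difference = 25×(1 − share×f), where f is the fraction of the effect that an exposed control receives.

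| Share exposed | f = 1 | f = 0.5 |
|---|---|---|
| 2.7% | 24.3 points | 24.7 points |
| 5.5% | 23.6 points | 24.3 points |
| 11.0% | 22.3 points | 23.6 points |

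At f = 1 the control incidence would show as 40 − 0.027×25 = 39.3% to 40 − 0.11×25 = 37.3%.

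**4. Intervention side.** Screening is daily, so patients past 48 hours at the switch would mostly have been screened as controls already. Those still waiting to reach 48 hours number about 52/91×2 = 1.1 or 52/183×2 = 0.6. They enrol free of delirium, after rounds have begun.

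**The case against.** The strongest reply is that the plan never says rounds start the moment the 52nd control enrols. It says that enrolment and data collection both continue to the target, and control data include hospital stay and in-house mortality. It also says that controls have no routine psychiatric involvement. On that reading, control follow-up finishes first. This stands in part: an immediate switch is something the text permits, not something it states. But the only stopping condition named is the sample size, and the intent to keep controls unexposed is not backed by any rule that would do so.

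A reader might also infer that both groups are contaminated to a similar degree. With 10% misclassified on each side, 25 points would fall to 25×(1 − 0.1 − 0.1) = 20. The documents do not support this:

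- On the same accrual assumptions, the intervention side contributes about one patient.
- That patient's time before the switch precedes enrolment and is free of delirium. Bias could go either way, since the patient missed some preventive exposure but was also selected for having stayed well.
- The 20-point figure also assumes that every affected patient takes the full risk of the other condition. Controls exposed for part of their stay would not, and those already CAM-ICU positive cannot alter the primary outcome.

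Finally, a shift of 1 to 3 points is small beside an interval of ±17 points. That is true, and it limits the severity. It does not remove the case for the change: the error is systematic, it is avoidable, and it reaches the secondary outcomes as well.

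**Conclusion.** The gap is real and should be closed, but its likely effect is modest. As written, Sections 3.0 and 6.0 allow late-enrolled controls still in 7W to receive the intervention while counted as controls.

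Assuming 3 to 6 months of control accrual and 5 to 10 ICU days after enrolment, about 1 to 6 controls would be exposed. The primary difference would lose roughly 1 to 3 of its 25 points at full transfer of the effect, and less otherwise. Faster accrual or longer stays would raise these figures. The direction, toward zero, assumes that the intervention works. The effect on delirium duration, ventilation days and length of stay cannot be sized from the documents.

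The documents do not support a claim that both groups are materially contaminated, or that the switch is certain to be immediate.

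**What to change.** In Sections 3.0 and 6.0, state that:

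- psychiatry rounds begin only after the last enrolled control has left the ICU, by discharge or death;
- the intervention group includes only patients whose ICU admission falls on or after the first day of psychiatry rounds and who were not previously enrolled as controls;
- the switch date is recorded in the study database.

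The release point should be leaving the ICU, not a first positive CAM-ICU. At a first positive test the primary outcome is settled, but delirium duration, ventilation days, length of stay and mortality are still accruing.

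If a pause is impractical, pre-specify in Section 13.0 a sensitivity analysis that excludes patients present in the ICU on both sides of the switch. It also needs the recorded switch date.

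The cost is protocol wording and an enrolment pause of about one ICU stay. No extra patients or staff are needed.

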#### **4.0 DRUG/DEVICE INFORMATION**

Not applicable

#### **5.0 SELECTION AND WITHDRAWAL OF SUBJECTS**

Inclusion criteria are:

1. Patients who are  $\geq 18$  years of age
2. Patients admitted to the surgical ICU for  $>48$  hours OR
3. Patients admitted to the ICU  $<24$  hours who have been in the hospital  $>48$  hours OR
4. Patients who return to the ICU after being discharged from the ICU to the floor due a complication or need for higher acuity care.
5. Patients admitted to any surgical service who are receiving care in the 7 West surgical ICU, who are either medically or conservatively managed (non-surgical) or surgically managed as part of their care

Exclusion criteria are:

1. Patients in whom CAM-ICU cannot be performed (severe dementia, stroke or other neurological condition, encephalopathy, mental retardation, severe psychiatric disorder, vegetative state, severe traumatic brain injury, deaf/blind, etc.)
2. Patients who don't speak or understand English
3. Current alcohol or substance abuse
4. Patients who already have delirium within 24-48 hours of their ICU admission [Defined as a positive CAM-ICU test, or based on the *Diagnostic and Statistical Manual of Mental Disorders, Fifth Edition (DSM-V)* diagnostic criteria:

- Disturbance in attention (ie, reduced ability to direct, focus, sustain, and shift attention) and awareness.
- Change in cognition (eg, memory deficit, disorientation, language disturbance, perceptual disturbance) that is not better accounted for by a preexisting, established, or evolving dementia.
- The disturbance develops over a short period (usually hours to days) and tends to fluctuate during the course of the day.

- There is evidence from the history, physical examination, or laboratory findings that the disturbance is caused by a direct physiologic consequence of a general medical condition, an intoxicating substance, medication use, or more than one cause.]

Patients will be screened for eligibility on rounds daily. Patients may withdraw from the study at any point without impacting their healthcare.

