## **3.0 STUDY DESIGN**

This is a prospective, single institution, controlled, pilot study of patients admitted to the 7W ICU which will compare the incidence and delirium rates among patients undergoing routine care before

intervention (no routine psychiatric involvement) (control group) and patients after the intervention (psychiatry team rounding with the ICU team daily) (intervention group) . Randomization is not possible for this study; although block randomization was considered, it will result in sub-optimal data subject to bias.

A sample size of 104 (52 per group) is targeted based on an *a priori* sample size calculation. Patients will be screened on a daily basis for study eligibility by study personnel and ICU team members, before delirium develops. Patients in both groups will be given an information sheet, verbal consent will be obtained, and the patient's agreement to participate will be documented in the medical record. For patients who are unable to make their own decisions, the information sheet will be given to their designated healthcare decision maker, verbal consent will be obtained, and the healthcare decision maker's agreement will be documented in the medical record.

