## **12. DATA COLLECTION AND MONITORING**

Data which will be collected includes: age, gender, body mass index, history or alcohol or substance abuse, admitting diagnosis, dementia, comorbid conditions, admitting Sequential Organ Failure Assessment (SOFA) score, deliriogenic medications used during study enrollment, the interventions/medications used to treat delirium as designated by psychiatry in conjunction with the ICU team (in intervention group) and the ICU team (control group), and the number of days from ICU admission to study enrollment. Data on the incidence of ICU delirium, duration of delirium/mechanical ventilation, in-house mortality, and length of stay will also be collected.

Data will be collected using RedCap, a password protected website. No patient identifiers will be used. A copy of the information sheet will be provided to the patient and be placed in the patient's chart. We will retain a copy of the information sheet in a double locked storage office.

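### With no limit on prior ICU stay and no rule for patients already in the unit when a phase opens, the control-first order can lengthen control stay with no true effect

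*Combined protocol and SAP*

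**What the plan says.** **Entry.** Section 5.0, inclusion 2, takes "Patients admitted to the surgical ICU for" more than 48 hours. That is a minimum with no maximum. Inclusion 3, by contrast, has its own ceiling of 24 hours in the ICU. Inclusion 4 takes "Patients who return to the ICU after being discharged from the ICU to the floor due a complication or need for higher acuity care", again without a time limit.

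**Screening.** Section 5.0 states "Patients will be screened for eligibility on rounds daily", and section 3.0 states "Patients will be screened on a daily basis for study eligibility by study personnel and ICU team members, before delirium develops". Exclusion 4 removes "Patients who already have delirium within 24-48 hours of their ICU admission". I read these together as admitting only patients with no delirium so far.

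**Order.** Section 3.0 says of the controls: "Enrollment and data collection will continue for as long as it takes to reach the target sample size of 52 patients for this group". Section 6.0 continues: "We will then proceed to enroll patients into the intervention group, who undergo standard care". Unit and criteria are the same in both phases. No gap is stated, and there is no rule for patients who are in the unit on either opening day.

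**Outcomes and analysis.** ICU stay, hospital stay and ventilation duration are secondary outcomes. Section 13.0 assigns truncated negative binomial regression to stay and ANOVA to ventilation, without a time origin. Section 9.0, writing of patients who develop delirium, speaks of their total stay.

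**Safeguards.** Section 12 records "the number of days from ICU admission to study enrollment". Section 13.0 plans an inverse-probability-weighted comparison as a sensitivity analysis and lists no propensity covariates.

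**The concern.** On the first screening day of the control phase, every delirium-free patient already past 48 hours in 7W qualifies, provided the other criteria are met. A cross-section of current inpatients over-represents long stays, because a patient who stays longer is more likely to be there on any given day. By the time the intervention phase opens, the same unit has been screened daily for the whole control phase. Most comparable patients will have been enrolled already, and new entrants will mainly be those just reaching 48 hours.

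The two groups can therefore differ in stay because of how they were sampled. The direction favours psychiatry rounds, and the pilot's estimates are meant to feed the design of a larger trial. Incomplete enrolment in the first phase does not make this harmless: a long-stay patient missed then and enrolled later brings days spent under control conditions into the intervention group.

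**Working it through.** **Yardstick from the plan.** The plan gives no figure on this point. Its precision for the incidence difference (section 13.0) serves as a scale. With 40% versus 15% and 47 per group:

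0.25 ± 1.96 × √(0.40×0.60/47 + 0.15×0.85/47) = 0.25 ± 0.173, or 7.7% to 42.3%.

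This reproduces the stated 8%-42%, a half-width of about 17 points.

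**Stay counted from ICU admission, no effect.** From the documents: 52 per group and the 48-hour threshold. Assumed: stay = 2 days + exponential with mean 7; new entrants are enrolled as they pass 48 hours; k of the 52 controls come from the opening-day stock.

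- Mean stay of a new entrant: 2 + 7 = 9 days.
- Mean stay of a stock patient: length-biased sampling doubles the mean of the exponential part, so 2 + 14 = 16 days.
- Control mean: [(52 − k)×9 + k×16]/52 = 9 + 7k/52. Each stock patient adds about 0.13 day.

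| k | Control mean (days) | Intervention/control ratio |
|---|---|---|
| 1 | 9.13 | 0.985 |
| 4 | 9.54 | 0.94 |
| 5 | 9.67 | 0.93 |
| 10 | 10.35 | 0.87 |

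With a log-normal excess of the same mean (7 days, sigma 0.9), a stock patient's excess averages 7 × exp(0.81) = 15.7 days, so total stay is 17.7. The ratio is 9/9.84 = 0.915 for k = 5 and 9/10.68 = 0.84 for k = 10.

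**How large might k be?** Two consecutive 52-patient phases were simulated with no effect. Assumed: 4 to 20 eligible patients past 48 hours; log-normal stay (median 5 days, log-SD 0.9, kept if over 2 days); entry only while delirium-free; control incidence about 31-41%.

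- Every eligible patient enrolled at the first screen: about 1-7 of 52 controls are stock, and mean control stay is 0.1-1.1 days longer (about 9.3-10.2 versus 9.1).
- 30% enrolled per day: about 1-4 are stock, and the gap is 0.1-0.9 day.
- Incidence of only about 11-15%: stock up to 12, gap up to 2.6 days. This lies well below the plan's 40%.
- Entry capped at 3.5 days after ICU admission (illustrative): stock of 1 or fewer, gap within about 0.1 day.

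**Stay counted from enrolment.** Under the exponential model, remaining stay averages 7 days for stock and new entrants alike, so the ratio is 1.00. Under the log-normal, a stock patient's remaining stay averages 15.7/2 = 7.9 days. With k = 10 the control mean is (42×7 + 10×7.9)/52 = 7.17, and the ratio is 7/7.17 = 0.98.

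**Incidence.** Assume a daily hazard falling from 12% to 3%, with 12% leaving per day. Incidence is then 37% for entry at 48 hours and 25% for entry three days later. That 12-point contrast is between kinds of patient. Between groups it is 12 × 5/52 = 1.2 points (k = 5) or 12 × 10/52 = 2.3 points (k = 10), with controls lower. The simulation gave about 0 with a constant hazard and 0 to 1.8 points, controls lower, with a declining one.

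Ventilation days were not computed.

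**The case against.** The strongest case against has four parts.

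- **Same criteria in both phases.** A reader might infer that the intervention phase takes no long-stay patients. The documents do not say so. Returns to the ICU, patients missed earlier and late consents can all enter after a long stay, and any pause between phases would rebuild a stock. This stands: fewer is a fair inference, none is not.
- **The stock may be small.** Stock patients must be free of delirium, English-speaking, testable with the CAM-ICU, without current alcohol or substance abuse, and willing. This stands as a reason to start the range at 1. It does not remove the direction of the bias.
- **The stay bias depends on an unstated time origin.** This also stands: counting from enrolment removes nearly all of it. But the plan does not specify that origin, and the reference to total stay in section 9.0 points the other way.
- **Safeguards exist.** Entry lag is recorded and compared between groups, and a weighted analysis is planned. These help only in part. Lag is not a named covariate, the main stay analysis is not described as adjusted, and weighting is unreliable if long lags occur almost only among controls.

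A reader might also infer that the primary comparison is biased in favour of psychiatry rounds. The calculation does not support that: the shift is small beside the planned interval and, where it appears, lowers control incidence. The hazards behind it are assumptions, with no source in the documents.

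**Conclusion.** The point holds for length of stay, a secondary outcome, and by the same mechanism probably for ventilation days. Followed as written, with stay counted from ICU admission, the design can lengthen control stay under no effect. The null ratio of mean stay is about 0.985 with 1 stock patient and 0.87 with 10, assuming a mean stay of 9 days; a heavier-tailed distribution takes the latter to 0.84. The direction is clear. The size is not, because the documents give no bed count, census, stay distribution or enrolment rate. The effect on delirium incidence, about 0 to 2 points and not in the intervention's favour, is no reason to doubt the primary comparison. This is a modest, directional and cheaply avoidable bias in a pilot whose estimates will be carried forward.

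**What to change.** **Section 5.0, both phases:** enrol only patients whose qualifying time (the 48-hour ICU mark, the ICU transfer or the ICU return) falls after that phase opens, and within a fixed limit of that time. The sponsor should set the limit with room for consent by a healthcare decision maker; no particular number of hours follows from the documents. Log patients already past the limit and do not enrol them.

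**Section 13.0:** count ICU stay, hospital stay and ventilation days from enrolment, and include days from ICU admission to enrolment as a covariate in the outcome models and the propensity model.

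**Cost:** protocol wording, a few patients lost at the start of each phase, and slightly slower accrual. Daily screening is already planned and the lag is already collected, so no new procedure or data item is needed beyond the log.

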The aim of our study is to determine the effect of delirium prevention care bundle protocols and a multi-disciplinary care model rounding with a psychiatry team (intervention group) on the incidence of delirium as compared to a group undergoing standard care without psychiatry participating in ICU rounds (control group). The psychiatric intervention entails a multidisciplinary approach to patient care during rounds, working with the ICU team to make recommendations on non-pharmacological and pharmacological prevention and treatment strategies for patients who are positive for delirium, and helping to differentiate delirium from other psychiatric conditions, that the ICU team may not have the training background to easily identify. Since the incidence of ICU delirium is so high and it has negative ramifications on patient survival, long-term outcomes, cognitive function, and places a heavy burden on the healthcare system and cost, preventative strategies are desperately needed. Using bundle care protocols and multidisciplinary rounding with psychiatry may be a feasible and cheap measure to help prevent delirium in ICU patients.

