## **10.0 CRITERIA FOR EVALUATION AND ENDPOINT DEFINITIONS**

Primary outcome: incidence of delirium, defined by a positive CAM-ICU.

Secondary outcomes: delirium duration, ICU/hospital length of stay, in-hospital mortality, and mechanical ventilation duration.

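### Psychiatry joins the screening rounds only in the intervention phase and is not kept out of eligibility decisions, so delirium incidence there can fall without any prevention

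*Combined protocol and SAP*

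**What the plan says.** **Entry rule.** Exclusion 4 in Section 5.0 removes "Patients who already have delirium within 24-48 hours of their ICU admission". Delirium for this purpose is "Defined as a positive CAM-ICU test, or based on the *Diagnostic and Statistical Manual of Mental Disorders, Fifth Edition (DSM-V)* diagnostic criteria", so either route is enough.

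**Screening.** Section 5.0 places it on rounds: "Patients will be screened for eligibility on rounds daily". Section 3.0 names the screeners: "Patients will be screened on a daily basis for study eligibility by study personnel and ICU team members, before delirium develops".

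**Who is on rounds.** The groups are sequential. Section 6.0 says that control patients receive the standard bundle "but will not have routine psychiatric involvement in care". In the intervention phase, Section 3.0 adds "a member of the psychiatric team (attending, resident, and/or fellow) participating in daily (Monday-Friday) multidisciplinary rounds with the ICU team". Section 1.0 gives psychiatry a diagnostic role: "helping to differentiate delirium from other psychiatric conditions, that the ICU team may not have the training background to easily identify".

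**Endpoint.** Section 10.0 uses one route only: "Primary outcome: incidence of delirium, defined by a positive CAM-ICU". The test is given by the bedside nurse in the same way in both phases (Section 3.0).

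**What is recorded.** The data lists in Sections 3.0 and 12 cover characteristics such as age, dementia, comorbid conditions, admission SOFA score and days from ICU admission to enrolment. They include no DSM-5 assessment at entry. The protocol describes no screening log and no count of exclusions by route or phase.

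**The concern.** The entry rule is wider than the endpoint rule, and the extra width rests on clinical judgement. The intervention puts a specialist in that judgement where and when eligibility is decided, in one phase only. The ICU screeners may formally make the decision, but in the intervention phase they can make it after hearing psychiatry's opinion.

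Take a patient with early delirium whose CAM-ICU is still negative. In the control phase that patient may be enrolled, turn CAM-ICU positive and count as an event. In the intervention phase the same patient can be excluded through the DSM-5 route. Incidence then differs between phases because different patients entered.

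Section 13.0 says that the pilot exists to estimate the base incidence and the size of the effect for a larger trial. An artefact of this kind would pass directly into that trial's assumed effect and sample size.

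**Working it through.** **1. The plan's own figures.** Inputs from Section 13.0: base incidence 40%, reduction 25%, 47 per group, stated interval for the difference 8%-42%.

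- Read as 25 points (40% to 15%): SE = √(0.40×0.60/47 + 0.15×0.85/47) = 0.0884, and 0.25 ± 1.96×0.0884 gives 7.7% to 42.3%. This reproduces the stated interval.
- Read as a relative 25% (40% to 30%): SE = √(0.40×0.60/47 + 0.30×0.70/47) = 0.0978, and 0.10 ± 1.96×0.0978 gives -9.2% to 29.2%. This does not.

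The planned difference is therefore 25 percentage points, and any bias should be measured against that.

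**2. Model.** Assume no true effect and 40% incidence under control-phase screening. Let f be the share of otherwise eligible patients removed in the intervention phase because of psychiatric input, and s the share of those who would later have turned CAM-ICU positive. Then

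- intervention incidence = (0.40 − f·s)/(1 − f)
- spurious fall = f·(s − 0.40)/(1 − f)

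The fall is positive only if s exceeds 40%, that is, if the removed patients are at higher risk than average. That is plausible for early delirium, but the documents give neither f nor s.

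**3. Results.** Illustrative range: f = 5-15%, s = 60-80%.

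| f | s | Intervention incidence | Spurious fall (points) | Share of 25 points |
|---|---|---|---|---|
| 5% | 60% | 0.370/0.95 = 38.9% | 1.1 | 4% |
| 5% | 80% | 0.360/0.95 = 37.9% | 2.1 | 8% |
| 10% | 60% | 0.340/0.90 = 37.8% | 2.2 | 9% |
| 10% | 80% | 0.320/0.90 = 35.6% | 4.4 | 18% |
| 15% | 60% | 0.310/0.85 = 36.5% | 3.5 | 14% |
| 15% | 80% | 0.280/0.85 = 32.9% | 7.1 | 28% |

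Incomplete detection lowers f. Suppose 10% of eligible patients had missed delirium and only five days in seven counted. Then f = 0.10×5/7 = 7.1%, and the fall is 0.0714×0.20/0.9286 = 1.5 points (s = 60%) to 0.0714×0.40/0.9286 = 3.1 points (s = 80%).

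**4. Effect on the test.** With 52 per group, a two-sided 5% test and no true effect, the chance of a significant result in favour of the intervention is nominally 2.5%. By the normal approximation it becomes about 3.2% at the smallest case in the table and 11.2% at the largest.

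**5. Upper bound.** Even with s = 100%, a spurious fall of the full 25 points needs f = 0.25/(0.60 + 0.25) = 29%. This mechanism alone is not a credible source of the whole planned effect.

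**6. Can the analysis recover it?** Section 13.0 plans multivariable logistic regression and, as a sensitivity analysis, inverse probability weighting on a propensity score. Both work on enrolled patients and recorded covariates. The affected patients are missing from one group, and the feature that separates them, delirium at entry not detected by CAM-ICU, is not collected. Neither method can restore the balance.

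**The case against.** Several objections have force.

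- **Psychiatry is not a named screener.** Section 3.0 lists study personnel and ICU team members, and psychiatry attends on weekdays only. A reader might infer that psychiatry applies the DSM-5 route, or that delirium is in fact screened out more thoroughly in the intervention phase. The documents say neither. They leave the influence possible and unrecorded.
- **The diagnostic role concerns other disorders.** Sections 1.0, 3.0, 6.0 and 7.0 speak of telling delirium from other psychiatric conditions. None says that the ICU team misses delirium in CAM-ICU-negative patients. Better differential diagnosis could also rescue patients whom the ICU team would have excluded wrongly under DSM-5, for example those whose disturbance reflects dementia. If their risk were like that of the removed patients, only the net share removed would matter, and the bias would shrink. This is why the direction is likely rather than established. For exclusion 1, which concerns whether CAM-ICU can be performed, no direction can be argued.
- **The affected group is narrow.** The exclusion concerns the first 24-48 hours in the ICU, and nurses test every morning in both phases. The patient must be CAM-ICU negative, flagged under DSM-5, excluded for that reason, and otherwise destined to turn positive. The largest case in the table needs 0.15×0.80 = 12 of the 40 control points, 30% of all control events, to come from such patients.
- **It is a pilot that acknowledges non-randomised groups.** That is true, but the planned adjustment does not reach this mechanism, and estimating the effect is one of the pilot's stated purposes.

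**Conclusion.** The concern holds as a gap in the plan. As written, the intervention can influence who enters the study, through an assessor-dependent exclusion that the endpoint does not share, and the planned analyses can neither detect nor correct it. The likely direction favours the intervention.

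The illustrative size is about 1-7 percentage points. It rests on three assumptions: a 40% base rate (Section 13.0), no true effect, and values of f and s that the documents do not supply. Less complete detection gives less.

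Two stronger readings should be set aside. A reader who took the planned reduction as relative would compare 1-7 points with 10 and conclude that the artefact could be 10-70% of the target. The stated 8%-42% interval rules that reading out, and against 25 points the share is 4-28%. A reader might also conclude that the DSM-5 route must be deleted. That does not follow, because the problem is unequal application between phases, and deletion would knowingly enrol patients with diagnosed delirium into an incidence study.

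**What to change.** In Section 5.0, state that in both phases the same study personnel or ICU screeners apply exclusions 1 and 4 by the same procedure, and record the eligibility decision before any psychiatric input on that patient. State that later psychiatric findings do not reverse eligibility and are recorded as a descriptor. The DSM-5 route may stay if it is applied identically in both phases.

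In Section 12, add a screening log. In Section 13.0, commit to reporting exclusions by reason, by route (CAM-ICU or DSM-5) and by phase. The log needs to cover the control phase from its first screened patient, since the comparison between phases is what shows whether screening was alike.

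The cost is protocol wording, a little more screening record-keeping, and the enrolment of a few patients whom psychiatry would have flagged. The target of 104 and the stated precision do not change.
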